1.20.1 RESCUE MEDICINE

N/A

STUDY INTERVENTION DISCONTINUATION AND PARTICIPANT DISCONTINUATION/WITHDRAWAL

Participants may withdraw voluntarily from the study or the PI may discontinue a participant from the study. This section should state which adverse events would result in discontinuation of study intervention or participant discontinuation/withdrawal. In addition, participants may discontinue the study intervention, but remain in the study for follow-up, especially for safety and efficacy study endpoints (if applicable). Consider requiring separate documentation for study intervention discontinuation and participant discontinuation/withdrawal from the study. In addition, a dedicated Case Report Form (CRF) page should capture the date and the specific underlying reason for discontinuation of study intervention or participant discontinuation/withdrawal.

1.21 DISCONTINUATION OF STUDY INTERVENTION

If a patient notes a possible adverse effect, such as allergic reaction to study medication, we will discontinue study medication. Any new clinically relevant finding will be reported as an adverse event (AE). Because the outpatient course of study medication is only 6 days, we will not restart study

medication in that short timeframe and instead will withdraw the patient from this study. Such patients will still be offered planned follow up and the planned outcome measures will still be collected.

The data to be collected at the time of study intervention discontinuation will include the following:

• Details of possible adverse event, and appropriate care as indicated (for example ER assessment).

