1.6 RISK/BENEFIT ASSESSMENT

1.6.1 KNOWN POTENTIAL RISKS

Risks from medication: NAC is FDA approved, with a forty-year safety history. It is widely used for nebulized delivery to the lower airways for its mucolytic effects (Mucomyst). Otolaryngologists have prescribed NAC off-label as a topical nasal medication for years for certain chronic rhinosinusitis patients for it mucolytic effects, with no safety concerns reported. It also has a long history of systemic oral administration safely. It is used at high dose orally in emergency departments for acetaminophen overdose, to prevent hepatotoxicity. Known side effects reported from nebulized pulmonary delivery include some patients reporting a noticeable odor. Other possible side effects might include local irritation; however it has been used widely in the lower airways and via tracheostomy stoma without irritation. There are rare reports of bronchospasm reactions to NAC delivered to the lower airways via nebulizer; these typically respond to bronchodilators (albuterol). Loading doses for FDA-approved oral administration of NAC are about 55 ml of 20% NAC solution (≈10 g), and our study patients will receive a 4 g loading dose, much lower. Importantly, a recent published study using the identical oral NAC regimen proposed here reported no adverse events or treatment side effects³. NAC can cause headache or potentiate effects of nitroglycerine or isosorbide. It may alter levels of homocysteine. It may potentiate the effects of certain immunosuppressants, such as cyclophosphamide or azathioprine. It can cause GI upset.

Other risks: There is no economic risk, as we will supply the study medication. The pre-study work up and care is the trauma standard-of-care, unchanged, and is no different for patients choosing or not choosing to participate in this study. Psychologically, there is the risk of disappointment from possible lack of improvement or from treatment with placebo. However, the current standard-of-care is **no treatment**, so we will council patients regarding this.

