1.22 PARTICIPANT DISCONTINUATION/WITHDRAWAL FROM THE STUDY

Participants are free to withdraw from participation in the study at any time upon request.

An investigator may discontinue or withdraw a participant from the study for the following reasons:

- Pregnancy
- Significant study intervention non-compliance
- If any clinical adverse event (AE), laboratory abnormality, or other medical condition or situation occurs such that continued participation in the study would not be in the best interest of the participant
- If the participant meets an exclusion criterion (either newly developed or not previously recognized) that precludes further study participation

The reason for participant discontinuation or withdrawal from the study will be recorded on the NAC Case Report Form (CRF). Subjects who sign the informed consent form and are randomized but do not receive the study intervention may be replaced. Subjects who sign the informed consent form, and are randomized and receive the study intervention, and subsequently withdraw, or are withdrawn or discontinued from the study, will be replaced. Patients who do not complete the full course of study drug/placebo will be noted in the results tables, and they will not be included in the statistical analysis of outcome measures, since this is a simple comparison of SIT score between patients receiving a 1 week course of NAC versus placebo.

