1.26.8 EVENTS OF SPECIAL INTEREST

In an effort to minimize failure to follow up, we will give the subject the option If for any specific reason will not be able to attend the Visit 2 and Visit 3 in person we will mail by Certified Mail the full Smell identification Test and the QOD questionnaire and request to be send back to us in the same way (Certified Mail will be cover by the Investigator).

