- Anticipated impact of dropout rates, withdrawal, missing data, etc. on study power: to compensate for such issues, we have increased our sample size by 5 subjects per group.
- Secondary endpoint: We have included a secondary endpoint to measure quality of life via a
 validated questionnaire (QOD). We have no specific guides for mean or variance for the
 questionnaire in terms of possible NAC or placebo treatment, so no calculations are possible.
 Nonetheless, a simple questionnaire poses no cost or risk, such that we see no reason to not
 collect these data.

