1.30 POPULATIONS FOR ANALYSES

• Intention-to-Treat (ITT) Analysis Dataset (i.e., all randomized participants):

Placebo group (n=30) NAC treated group (n=30)

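### Section 1.22 drops everyone who does not finish the course from the outcome analysis and replaces dosed withdrawals, while Section 1.30 names only an all-randomized ITT set

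*Combined protocol and SAP*

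**What the plan says.** Four rules bear on a patient who is randomized and then stops.

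- **Exclusion (Section 1.22).** Patients who do not complete the full course are noted in the results tables, but "they will not be included in the statistical analysis of outcome measures". The stated reason is that the trial simply compares SIT between patients who received a week of NAC or placebo.
- **Replacement (Section 1.22).** Dosed participants who "subsequently withdraw, or are withdrawn or discontinued from the study, will be replaced". Those randomized but never dosed may be replaced.
- **Stopping for a possible adverse effect (Section 1.21).** The site will not restart "medication in that short timeframe and instead will withdraw the patient from this study". The next sentence adds: "Such patients will still be offered planned follow up and the planned outcome measures will still be collected".
- **Analysis set (Section 1.30).** The only set named is "Intention-to-Treat (ITT) Analysis Dataset (i.e., all randomized participants", with 30 printed for each group.

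Sections 1.31 to 1.31.3 specify two-tailed t-tests but name no population. No per-protocol or modified ITT set is defined. For losses, Section 1.29 says "we have increased our sample size by 5 subjects per group". Section 1.26.8 provides that for a subject who cannot attend, "we will mail by Certified Mail the full Smell identification Test and the QOD questionnaire".

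**The concern.** Sections 1.22 and 1.30 disagree as soon as one patient stops, and nothing says which prevails. Section 1.22 is the more explicit, and following it means analysing completers only. Removing people after randomization can bias the NAC minus placebo difference if stopping differs by arm and is related to SIT.

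Two features make this worse. *Full course* is not defined, although Section 1.16.2 lets a late-noted dose be skipped, so it is unclear whether one skipped dose excludes a patient. Also, the drug log that shows completion is collected at the first outpatient visit (Section 1.19), which is the visit of the 1-month SIT (Section 1.3). Who is excluded can therefore be settled with an outcome already in hand. Blinding limits that risk but does not remove it.

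For patients stopped for a possible adverse effect, the trial will collect SIT and QOD and then leave them out of the test. For other non-completers (non-compliance, pregnancy, a newly met exclusion criterion, missed doses) the documents do not say that outcomes are collected after withdrawal, so there the gap is in follow-up as well as in analysis.

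**Working it through.** **The plan's own figure.** Inputs from Sections 1.29 and 1.31: means 17 and 25 (difference 8), SD 10, two-sided alpha 0.05, power 0.80. Then n = 2 × (1.96 + 0.842)² × 10² / 8² = 24.5, so 25 per arm; 25 + 5 = 30. The stated size reproduces and is not in dispute. By noncentral t, power is 86% at 30 per arm and 79% at 25.

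**The conflict by counting.** Suppose one dosed patient stops and is replaced, so that 61 are randomized. The definition in Section 1.30 gives 61 to analyse, its printed counts give 60 including or excluding nobody in particular, and Section 1.22 gives 60 without the stopper.

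**Bias of a completers-only comparison.** Let p be an arm's stop rate and g its completer-minus-stopper gap in mean SIT. The arm mean is the completer mean minus p × g, so the completer mean overstates the arm mean by p × g. The bias in the difference is p(NAC) × g(NAC) − p(placebo) × g(placebo). With one common gap it is (p(NAC) − p(placebo)) × g.

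The documents give no stop rates or gaps, so those below are assumptions. With SD 10 and 30 completers per arm after replacement, SE = 10 × √(2/30) = 2.58. Rejection rates use the noncentral t with 58 df and no true effect.

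| Stop rate, NAC v placebo | Gap | Bias (points) | Type I error |
|---|---|---|---|
| Equal | equal | 0 | 5% |
| 10% v 5% | 5 | 0.05 × 5 = 0.25 | 5.1% |
| 20% v 5% | 10 | 0.15 × 10 = 1.5 | 8.8% |
| 20% v 0% | 10 | 0.20 × 10 = 2.0 | 11.9% |

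If placebo has the higher rate, the signs reverse. A true 8-point effect would then appear as 8 − 1.5 = 6.5 or 8 − 2.0 = 6.0, and power falls from 86% to 70% or 63%.

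**What keeping the scores achieves.** Let a share r of stoppers return a SIT, and assume they are typical of stoppers. The residual shift in an arm is p × g − g × p × r / ((1 − p) + p × r). For 20% v 0%, gap 10, 30 randomized per arm (type I error by simulation):

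| Share returning | Residual bias | Type I error |
|---|---|---|
| 100% | 0 | about 5% |
| 75% | 2 − 1.5/0.95 = 0.4 | about 5.4% |
| 50% | 2 − 1/0.9 = 0.9 | 6.3% |
| 0% | 2.0 | about 11% |

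**What it costs in power.** Suppose stopped NAC patients gain nothing. The difference becomes 8 × 0.9 = 7.2 at 10% stops or 8 × 0.8 = 6.4 at 20%. Power is then 78% or 68% with 30 scores per arm, and 70% or 60% with 25.

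**The case against.** The exclusion in Section 1.22 is deliberate and comes with a reason. Sections 1.31 to 1.31.3 never tie the t-test to the ITT set, so Section 1.22 is the only sentence saying who enters the outcome analysis, and the label in Section 1.30 could be read as the slip. Non-completers are disclosed in the results tables, and Section 1.31.8 plans an individual-data table. What a phase 2 trial should make primary is partly a judgment. The larger bias figures need 15 to 20 percentage points of differential stopping and a gap of a full SD, in a blinded one-week course whose regimen is described as free of adverse effects (Sections 1.6.1, 1.9). Keeping stoppers also has a price: in the mild 10% v 5% case, up to 8 percentage points of power buys back 0.1 percentage point of type I error.

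Much of this stands. The sizes are assumptions, and few patients may stop. But the reason given describes a completers' question; it does not make that comparison ITT or give it the protection of randomization. Tables that list non-completers do not put them in the test.

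A reader might also infer that the rule favours NAC, because the protocol says of NAC that "It can cause GI upset" and lists headache as an effect. The documents do not support a direction: Sections 1.6.2 and 1.9 report benefit on headache after TBI with this regimen, so either arm could lose more patients.

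**Conclusion.** The point holds. Section 1.22 and Section 1.30 cannot both be applied to a randomized patient who stops, and following Section 1.22 gives a completers-only test that is not the stated ITT. This should be settled before unblinding. It needs only one stop to arise and rests on the text alone.

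The effect on the result is unknown in direction and size. Under the assumed rates and gaps it runs from 0.25 points (type I error 5.1%) to 2.0 points (11.9%), or to a comparable loss of power if placebo loses more, and it is zero when rates and gaps match across arms.

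Two stronger readings are tempting but unsupported. One is that the plan collects and then discards the scores of every non-completer: Section 1.21 promises continued collection only after a possible adverse effect. The introductory text on discontinuation says only that participants may remain for follow-up, and it reads as unedited template wording. The other is that the sample size is wrong: it reproduces. Nor is the decision to stop drug on suspicion of an adverse effect in question; that is a safety choice.

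**What to change.** 1. **Sections 1.21 and 1.22.** Record stopping drug for any reason as *study drug discontinued, follow-up continues*, unless the patient withdraws consent for follow-up. Collect SIT and QOD at 1 and 3 months at the planned visits or by the mail option in Section 1.26.8.
2. **Section 1.22, exclusion.** Replace the sentence with: *Non-completers are noted in the results tables and stay in their randomized arm; all collected SIT and QOD scores enter the primary and secondary analyses; a completers-only comparison is a sensitivity analysis.* Define the full course, given that Section 1.16.2 allows skipped doses.
3. **Section 1.22, replacement.** Do not replace participants for stopping drug when their outcomes are collected. Anyone added is additional and does not substitute for the original participant; the same applies to those randomized but not dosed.
4. **Sections 1.30, 1.31.2 and 1.31.3.** State one set: all randomized participants, analysed as randomized, using all available scores at each visit. Drop the fixed 30 as part of the definition. Report missing scores and drug stops by arm, with reasons.

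The cost is text edits, one CRF status, and a small follow-up effort for patients stopped for reasons other than adverse effects. Adverse-effect stops need no new visits. The statistical downside is the dilution shown above. Additional participants can restore the number of scores but lengthen recruitment. Protection against bias is full only if stoppers return a SIT.

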1.22 PARTICIPANT DISCONTINUATION/WITHDRAWAL FROM THE STUDY

Participants are free to withdraw from participation in the study at any time upon request.

An investigator may discontinue or withdraw a participant from the study for the following reasons:

- Pregnancy
- Significant study intervention non-compliance
- If any clinical adverse event (AE), laboratory abnormality, or other medical condition or situation occurs such that continued participation in the study would not be in the best interest of the participant
- If the participant meets an exclusion criterion (either newly developed or not previously recognized) that precludes further study participation

The reason for participant discontinuation or withdrawal from the study will be recorded on the NAC Case Report Form (CRF). Subjects who sign the informed consent form and are randomized but do not receive the study intervention may be replaced. Subjects who sign the informed consent form, and are randomized and receive the study intervention, and subsequently withdraw, or are withdrawn or discontinued from the study, will be replaced. Patients who do not complete the full course of study drug/placebo will be noted in the results tables, and they will not be included in the statistical analysis of outcome measures, since this is a simple comparison of SIT score between patients receiving a 1 week course of NAC versus placebo.

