1.23 LOST TO FOLLOW-UP

A participant will be considered lost to follow-up if he or she fails to return for the 2 scheduled follow up Otolaryngology clinic visits and is unable to be contacted by the study site staff.

The following actions must be taken if a participant fails to return to the clinic for a required study visit:

- The site will attempt to contact the participant and reschedule the missed visit within 2 weeks and counsel the participant on the importance of maintaining the assigned visit schedule.
- Before a participant is deemed lost to follow-up, the investigator or designee will make every
 effort to regain contact with the participant (where possible, 3 telephone calls and, if necessary,
 a certified letter to the participant's last known mailing address or local equivalent methods).
 These contact attempts should be documented in the participant's medical record or study file.
- Should the participant continue to be unreachable, he or she will be considered to have withdrawn from the study with a primary reason of lost to follow-up.

In an effort to minimize failure to follow up, we will incentivize subject with a \$50 payment, to be provided at the follow up visits.

STUDY ASSESSMENTS AND PROCEDURES

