1.31.2 ANALYSIS OF THE PRIMARY EFFICACY ENDPOINT(S)

Primary endpoint is SIT score at 1 month and 3 months.

Placebo and NAC-treated groups will be compared. SIT (mean ± sd) will be compared via two-tailed t-test.

SIT scores may range from 0-40, and normal scores are well-established. An assignment of normosmia, mild hyposmia, moderate hyposmia, severe hyposmia, anosmia, or probable malingering can be made based on SIT score.

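### The plan gives two incompatible populations for the primary SIT test: all randomized (1.30) and full-course completers only (1.22)

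*Combined protocol and SAP*

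**What the plan says.** All references are to the combined protocol and SAP.

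- **1.30 (populations):** the only set listed is "Intention-to-Treat (ITT) Analysis Dataset (i.e., all randomized participants"), shown with n=30 per arm. No per-protocol, modified ITT or completers set is defined.
- **1.22 (withdrawal):** patients who do not complete the full course "will be noted in the results tables", and "they will not be included in the statistical analysis of outcome measures". The reason given is that the trial is a simple comparison of patients who received the one-week course. Patients who were randomized and dosed "and subsequently withdraw, or are withdrawn or discontinued from the study, will be replaced".
- **1.31.2 (primary analysis):** "Placebo and NAC-treated groups will be compared" by two-tailed t-test on SIT. No population is named. Sections 1.31.1 and 1.31.3 name none either.
- **1.21 (stopping study drug):** after a possible adverse effect the team will not restart drug and "instead will withdraw the patient from this study". It then adds: "Such patients will still be offered planned follow up and the planned outcome measures will still be collected".
- **1.23 (loss to follow-up):** for a patient who stays unreachable, "he or she will be considered to have withdrawn from the study with a primary reason of lost to follow-up".

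**The concern.** Once one randomized patient fails to finish the course, 1.30 and 1.22 cannot both be followed. Because the t-test sections name no set, two analysts working from this plan could test different patients.

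The two readings also differ in quality. All-randomized keeps the comparison that randomization created. The 1.22 reading selects patients on something that happens after randomization and that treatment may affect. The clearest route is in the text itself. A patient who stops for a possible adverse effect is withdrawn (1.21), then replaced and left out (1.22), although the outcome scores are still collected. Section 1.6.1 lists GI upset and headache as possible effects of NAC, so unequal stopping between arms is plausible. Missed outpatient doses and voluntary withdrawal are further routes.

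**Working it through.** **The plan's own sample size.** Inputs from 1.29 and 1.31.1: difference 25 − 17 = 8, SD 10, two-sided alpha 0.05, power 0.80. Normal approximation: n = 2 × (1.960 + 0.842)² × 10² / 8² = 24.5, so 25 per arm. Adding 5 per arm for dropout, withdrawal and missing data gives 30 per arm, 60 in total, as stated. With the noncentral t, power is 0.861 at 30 per arm and 0.791 at 25.

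**Bias from excluding non-completers (illustration).** Assume k of 30 NAC patients are excluded, their mean SIT differs by g points from that of the other NAC patients, and exclusion on placebo is unrelated to SIT. The mean of the remaining NAC patients then differs from the mean of all NAC patients by (k/30) × g. The sign can go either way.

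The table uses a two-sided t-test with SD 10 and 30 analysed per arm (that is, with replacement). Type I error applies if the bias favours NAC. Power for a true 8-point effect applies if the bias goes against NAC, and is evaluated at 8 minus the bias.

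| k | g | Bias | Type I error | Power |
|---|---|---|---|---|
| 0 | – | 0 | 5.0% | 0.861 |
| 1 | 5 | 0.17 | 5.05% | 0.85 |
| 1 | 10 | 0.33 | 5.2% | 0.83 |
| 2 | 5 | 0.33 | 5.2% | 0.83 |
| 2 | 10 | 0.67 | 5.7% | 0.80 |
| 5 | 5 | 0.83 | 6.16% | 0.779 |
| 5 | 10 | 1.67 | 9.73% | 0.674 |

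Without replacement (25 per arm, k = 5), type I error is 5.96% and 8.90%, and power falls from 0.791 to 0.70 and 0.59. A simulation that holds the total NAC SD at 10, so that completers have SD 9.8 or 9.3, gives similar results at 30 per arm: 6.2% and 10.0%, and power 0.79 and 0.70.

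**Power cost of analysing everyone randomized.** Assume a fraction q of NAC patients do not complete and gain nothing, with SD 10 within each subgroup. The mean difference is 8(1 − q) and the NAC SD is √(100 + 64q(1 − q)).

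- q = 10%: difference 7.2, NAC SD 10.28. Simulated power is 0.77 at 30 per arm; 33 per arm gives 0.81.
- q = 16.7% (5/30): difference 6.67, NAC SD 10.43. Simulated power is 0.70 at 30 per arm; 38 per arm gives 0.80.
- If every non-completer is replaced and everyone is kept, the numbers per arm are 30/0.9 = 33.3, so 34, with power 0.82; and 30/(5/6) = 36, with power 0.78.
- If only 25 of 30 per arm have a score, power is 0.69 and 0.62, against 0.79 with full completion.

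**The case against.** The strongest case has four parts.

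1. **Section 1.22 can be read as the specific rule.** Section 1.30 is a bare list that does not use the word primary, whereas 1.22 refers to the outcome analysis directly, names SIT and gives a reason. The sample size also fits a completers reading: 25 per arm at the full effect, plus 5 for losses. An analyst could reasonably follow 1.22, and defining a completers set in 1.30 would remove the contradiction. This shows that the exclusion was deliberate. It does not make it sound, because the primary superiority test would then rest on post-randomization selection.

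2. **The size may be negligible.** The documents report no adverse events with this regimen in an earlier trial. One or two informative exclusions move type I error only to between 5.05% and 5.7%, and equally selective exclusion in both arms gives no net bias. This stands: the 9.7% and 0.67 are the far end of a range, and a 10-point gap is a full SD. The contradiction does not depend on them.

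3. **There are safeguards.** Randomization codes are held until the last patient has finished both visits (1.18), non-completers are reported (1.22), and individual data are tabulated (1.31.8). These narrow the risk. However, no passage requires the population to be fixed before unblinding, 1.18 unblinds individual patients after an SAE, and blinding does not prevent selection caused by treatment.

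4. **Follow-up after withdrawal is promised only in part.** The commitment in 1.21 covers patients stopped for a possible adverse effect, not the other withdrawals in 1.22. Some randomized patients may therefore have no score, and selection through missing data would remain. This stands, and is why the fix asks for missing scores to be reported by arm and visit.

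**Conclusion.** The concern holds and should be fixed before unblinding. The plan defines an all-randomized set and, for the same outcome measures, orders the exclusion of non-completers. Followed as written, 1.22 turns the primary SIT test into a completers comparison that 1.30 does not define. That conclusion comes from the text and needs no assumed rate.

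The numerical consequence does depend on assumptions, since the documents give neither a non-completion rate nor any link between non-completion and SIT. It ranges from almost nothing (1 or 2 exclusions) to a bias of 0.8 to 1.7 points at 5 of 30 NAC patients with a 5- to 10-point gap.

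Two secondary gaps are missing detail and do not carry the finding:

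- Section 1.16.2 lets some doses be skipped and 1.19 logs doses, but nothing says whether a course with skipped doses counts as full.
- Loss to follow-up counts as withdrawal (1.23), so dosed patients lost to follow-up are replaced under 1.22, while 1.29 already adds 5 per arm. Both may be intended, but the plan does not say so.

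**What to change.** - In 1.22, delete only the clause "they will not be included in the statistical analysis of outcome measures" and the reason attached to it. Keep the commitment to note non-completers in the results tables.
- State in 1.22, 1.30 and 1.31 that the primary comparison is of all randomized participants in their assigned arm, using every SIT and QOD score obtained whatever the adherence, including scores after study drug was stopped.
- Report the number without a score by arm and visit, and do not describe those patients as analysed.
- Label n=30 per arm in 1.30 as the planned number. Count replacements as additional randomized patients, keep the patients they replace in the analysis, and say whether replacement is intended on top of the 5 per arm in 1.29.
- Present the full-course comparison as a labelled supportive analysis, with full course defined for analysis before unblinding.

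**Cost.** The change is mainly wording and uses visits already planned, although post-withdrawal scores are assured only for the patients covered by 1.21. The real cost is power. If NAC non-completers gain nothing, power at 30 per arm with no missing scores is about 0.77 at 10% non-completion and 0.70 at 16.7%, against 0.86 with full completion. The plan should state this and either accept it or enrol more: about 33 or 38 per arm for 80%.
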